2.3 Timings

Date of start of recruitment:	August 2005 [®]
Date of end of recruitment:	25February2009
First interim analysis*	April 2011
Second interim analysis*	August 2013
Final analysis start*	September 2017
Actual number of subjects:	2513

* Analyses are due 2 and 4 years after last patient recruitment and at the end of the trial..

[®] A pilot site was open from Mar2005

2.4 Patient eligibility

INCLUSION CRITERIA

- Male between 40 - 75 years; *** AGE LIMIT REMOVED March 2006 now 18 years and over*** *** Planned 500 women entered for generalisability***
- at least 2cm from the gastro-oesophageal junction of circumferential BM (Histologically proven by intestinal metaplasia in at least one sample) *** LATER CHANGED TO 1CM *** *** also changed to or a past history of intestinal metaplasia *** **changed 4th Feb 2008 to no need for IM and tongues of Barrett's are enough for inclusion**
- able to give written informed consent.
- WHO activity profile of 0 or 1 i.e. fully active and self-caring

EXCLUSION CRITERIA

1. those with high grade dysplasia or carcinoma at enrolment;
2. medical conditions which would make endoscopy or completing the trial difficult including:
 - a) Frequent transient ischaemic attacks (3 or more) or severe cerebral vascular accident in the previous 6 months*
 - b) Severe respiratory disease with arterial oxygen saturation of less than 90% at rest

AspECT

A phase III randomised study of Aspirin and Esomeprazole chemoprevention in Barrett's metaplasia

Funded by CR-UK, MRC, UHL and NCI

ISRCTN No.85156844

- c) Severe ischaemic heart disease (exercise tolerance less than 100 yards or life expectancy < 4 years) or myocardial infarction in the previous 3 months

- d) Severe inflammatory bowel disease requiring at least one hospital admission of 5 days in the last year or bowels open > 6 times/day

* Patients answering yes to this criteria were eligible for the PPI-only (non-aspirin) randomisation.

- 3. Patients with absolute contraindications to PPIs, aspirin or their excipients i.e. allergies, ulcers, renal impairment or use of oral anticoagulants.

*** added

- 4. pregnant or lactating women ***

*** amended***

- Up to 100 previous aspirin users will be entered providing they agree to stop aspirin use if not randomised to it.

amended

- Patients not wishing to stop aspirin or who have an absolute contraindication to it can be randomised to the low/high PPI dose arms only and will be analysed for that comparison only

For patients on existing PPI therapy, there is no washout period.

Patients are allowed 6 months of another treatment option or a break from treatment for any 6 month period or 12 months in total over the entire trial length of up to 10 years.

2.5 Sample size

2.5.1 Sample size – estimates used

The conversion rate in the UK is 0.98% (95% CI = 0.67 to 1.39%) (this is higher in the UK than the USA) however to be cautious we have agreed on 0.76%/year (approximately half way between the UK and the USA).

Aspirin has a hazard ratio of 1.5 (33.3% effective) in preventing the colorectal cancer rate. Evidence from epidemiological studies suggests that aspirin may decrease BA rates with a hazard ratio of 1.6 to 10 (40 - 90%). While we believe that current evidence indicates that aspirin is at least equally effective in the prevention of oesophageal adenocarcinoma as colorectal cancer, the role of PPI is more difficult to estimate for the reasons given previously. Therefore we have chosen a hazard ratio of 1.4 (28% effective) to assess weaker therapeutic effects.

2.5.2 Sample Size – original statement

A total of 5000 patients (1250 in each intervention group) will allow us to detect a difference in conversion rates of 0.22% per year between the PPI and aspirin intervention. The sample size required was calculated (pre CSM involvement) using nQuery Advisor® Release 4.0 based on the following:

Patients will be recruited over 2 years and followed up for a further 8 years. Exponential time to conversion with a constant event rate of at least 0.76% per year

Conversion hazard ratio (drug response) of control to treatment is 1.4

Power = 80% (2-sided test at 5% level of significance).

No interaction between the effects of aspirin and PPI interventions.

A 10% loss to follow-up from Office of National Statistics flagging

A 20% non-compliance with medication

Calculations adjusted for competing causes of mortality. A further proportion may take their medication but be lost to follow-up as they do not return their questionnaire and/or attend for surveillance endoscopy. This will not affect the primary outcome as all cause mortality and conversion to BA will be assessed by the Office of National Statistics, which has almost complete follow-up of registered subjects (we have conservatively assumed a 90% follow-up rate).

2.5.3 Exploratory sample size statement October 2008

Due to protocol amendments and an expected restriction on the number of patients to be recruited, an exploratory sample size is presented at the request of the Funders. Since the trial will recruit until end Dec 2008 in the UK and possibly until the end of June in Canada rather than to the number calculated in the original sample size, this calculation should be considered as a guide to the power and treatment effect size the trial should achieve.

This exploratory sample size is calculated as per the original sample size, but with

- Annual rate of conversion of 1% (allowing for the composite primary endpoint of all cause mortality and conversion to adenocarcinoma and conversion to high grade dysplasia.)

Justification: Using the National Statistics figures for 2005 based on the age and gender structure of the first 2046 patients recruited to AspECT gives a mortality rate in a year of 1.16%.

Using the UK Barrett's conversion rate to adenocarcinoma of at least 0.98% per year without treatment for 60% of the sample and 40% with a lower conversion rate of 0.66% (due to being

AspECT

A phase III randomised study of Aspirin and Esomeprazole chemoprevention in Barrett's metaplasia

Funded by CR-UK, MRC, UHL and NCI

ISRCTN No.85156844

female, have tongues of Barrett's metaplasia or only 1cm of Barrett's, or being <45 years old. Differing rates are not published for these patients so a rate of two thirds the UK conversion rate has been used) ie 0.85% conversion rate without treatment over the whole sample.

No good estimates of rates for conversion to high grade dysplasia for the UK could be found.

In this population, it is unlikely that the event rate for the composite primary endpoint in the control arm will be less than 1%.

- HR as in colorectal cancer
- No adjustment for compliance
- the follow-up increased to 10 years

Apart from limited recruitment and checking the event rate using the age/sex structure, no information or estimates from the current trial are used.

A total of 2224 patients (196 events) (approximately 556 in each intervention group) will allow us to detect a difference in conversion rates of 0.34% per year between low dose and high dose PPI and aspirin or no aspirin. This sample size was calculated using ARTMENU in STATA release 10.0 based on the following:

- Patients will be recruited over 3 years and followed up for a further 10 years
- Exponential time to conversion with a constant event rate of at least 1% per year without treatment
- Conversion hazard ratio (drug response) of control to treatment is 1.5 (1 year conversion rate 1% no or standard treatment vs 0.66% in the treated patients)
- Power = 80% (2-sided test at 5% level of significance)
- No interaction between the effects of aspirin and PPI interventions
- A 10% loss to follow-up from Office of National Statistics flagging

2.6 Randomisation

Randomisation is by minimisation using age split into four groups and length of Barrett's metaplasia split into three groups. There is a random component, with the patient having an 80% chance of being assigned the treatment that reduces the imbalance.

Age

- 40-49
- 50-59
- 60-69

AspECT

A phase III randomised study of Aspirin and Esomeprazole chemoprevention in Barrett's metaplasia

Funded by CR-UK, MRC, UHL and NCI

ISRCTN No.85156844

70-75

Length of Barrett's metaplasia

≤3cm

>3 and ≤8cm

>8cm

Initially the trial accrued only males. From Sept 2005, there are separate minimisation routines running for males and females.

**** Change in 2007

Limit on age to be removed and Barrett's from 1cm to be included***

Then

Age

18-49

50-59

60-69

≥70

Length of Barrett's metaplasia

<2cm

≥2cm and ≤3cm

>3 and ≤8cm

>8cm

2.6.1 *** Change 25th Feb 2008 ***

IM to be added as stratification factor

Tongue of Barretts to be added as a level in length

Individuals participating only in the PPI randomisation are randomised in a separate routine (same stratification)

Gender already separate routine

Then

Age

18-49

50-59

60-69

≥70

Length of Barrett's metaplasia

Tongue of Barretts

<2cm

≥2cm and ≤3cm

AspECT

A phase III randomised study of Aspirin and Esomeprazole chemoprevention in Barrett's metaplasia

Funded by CR-UK, MRC, UHL and NCI

ISRCTN No.85156844

>3 and ≤8cm
>8cm
IM
Yes
No

2.6.2 Blinding

After randomisation, both the patient and the treating doctor knows what treatment the patient is receiving. There is no blinding of treatments. (The cost of placebo drugs was prohibitively expensive.)

2.7 Definition of Primary and Secondary Outcomes

Primary outcome is

- Time from randomisation date to conversion from Barrett's metaplasia to high grade dysplasia (event), or to adenocarcinoma of the oesophagus (event) or time to death from all causes (event) or time to last follow-up (no event)

I.e. the time is noted as the time from date of randomisation to high grade dysplasia, adenocarcinoma of the oesophagus or death, whichever is the earlier, with the survival time coded as an event. For patients who do not have one of these events of interest, the time from randomisation to date of last follow-up is calculated and the survival time coded as a censored event.

Secondary outcomes are

- Time from randomisation date to conversion from Barrett's metaplasia to high grade dysplasia (event) or time to last follow-up (no event) or event that precludes getting high grade dysplasia (for example death) (no event)
- Time from randomisation date to progression from Barrett's metaplasia to adenocarcinoma of the oesophagus (event) or time to last follow-up (no event) or event that precludes getting adenocarcinoma of the oesophagus (for example death) (no event)
- Time from randomisation date to death from all causes (event) or time to last follow-up (no event)
- Time from randomisation date to death from oesophageal cancer (event) or time to last follow-up (no event) or death from a cause other than oesophageal cancer (no event)
- Molecular markers to be identified at the end of the trial and used during analyses of collected blood and/or tissue samples
- Cost per oesophageal adenocarcinoma prevented

AspECT

A phase III randomised study of Aspirin and Esomeprazole chemoprevention in Barrett's metaplasia

Funded by CR-UK, MRC, UHL and NCI

ISRCTN No.85156844

- Cost per life year saved
- Molecular markers to be identified at the end of the trial and used with samples collected across time along with treatment information
- Cost per quality adjusted life saved
- Cardiac event from SAE (our best data on cardiac disease) and new tumours (a marker of aspirin resistance)
- For gender secondary, same outcome as for primary

AspECT

A phase III randomised study of Aspirin and Esomeprazole chemoprevention in Barrett's metaplasia

Funded by CR-UK, MRC, UHL and NCI

ISRCTN No.85156844

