#### 5.1 Evaluations during the study

All patients will be followed-up annually after study entry, and an annual Follow-Up Form completed. The patients should be asked about their disease and osteoporosis status and this should be recorded on the form. The Follow-Up Site staff are reminded to:

- a) Ask patients at each follow-up visit/call about any hospital admissions or event.

AND

- b) Check patient medical records for any hospital admissions or events which should be reported as a Serious Adverse Event.

Treatment or intervention for Barrett's since the previous follow-up should also be determined and recorded along with any concomitant medication that the patient may have taken.

The Patients may be followed up by telephone or in person at year 1, 3, 5, 7 and 9 (if patients re-consented) post randomisation. A Follow-Up Form must be completed on all occasions.

At year 2, 4, 6, 8 and 10 (if patients re-consented) post randomisation (+/- 3 months either side) patients will have an endoscopy to assess their Barrett's. The following forms must be completed at these time points:

Biopsy Sampling Form

Endoscopy and Pathology Form

Follow-up Form

If the final endoscopic procedure is performed later than 8 years + 3 months (for those patients that did not re-consent to additional follow up) or later than 10 years + 3 months (for those patients who did re-consent to additional follow up), or later than 28th February 2017 (the date of LPLV) + 3 months, then provided that the patient has agreed, trial biopsy samples and trial endoscopy & pathology data will be collected.

Patients whose trial medication dose changes or is temporarily suspended (see section 8.5) should be reported using the Change of Treatment Form.

Patients who are prescribed clopidogrel should be reported using the clopidogrel CRF.

Patients who become pregnant should be reported using the Pregnancy Notification Form. Pregnant or lactating women will not undergo endoscopy and may be given dispensation to stop drug therapy for a year. This should be discussed with the Trial Office. During the first trimester only Gaviscon should be taken, after this it is advised that Omeprazole is prescribed if required. Patients may re-start esomeprazole after a break of 1 year.

Patients who undergo colonoscopy or flexible sigmoidoscopy during the trial should be reported using the Bowel Screening Form.

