## 6.2 Withdrawal from endoscopy

If a patient absolutely cannot tolerate endoscopy every 2 years, or is removed by clinical decision from routine endoscopic screening, the patient may remain on trial medication (if clinically indicated) and remain on trial follow up as "withdrawn from endoscopic follow up". The Trial Office should be notified when a patient withdraws from endoscopic follow up and a File Note be created. The patient should still be seen by the local PI every 2 years even if not endoscoped.

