- Calculations adjusted for competing causes of mortality. A further proportion may take their medication but be lost to follow-up as they do not return their questionnaire and/or attend for surveillance endoscopy. This will not affect the primary outcome as all-cause mortality and conversion to BA will be assessed by the Office of National Statistics, which has almost complete follow-up of registered subjects (we have conservatively assumed a 90% follow-up rate).

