6.6 Description of Available Data

Primary endpoint – survival until adenocarcinoma, high grade dysplasia or death from any cause

There will be a time for every patient. For some of the patients who do not reach an endpoint, the survival time will be less than the trial duration due to loss to follow-up. The endpoint of death and diagnosis of Barrett's adenocarcinoma can be picked up in many cases from NHS digital but the endpoint of high grade dysplasia will be under represented due to those lost to follow-up.

The median follow-up will be described using the median of those without an event and the median using the reverse Kaplan-Meier method.

Kaplan-Meier curves will be drawn for all patients, then split by aspirin intervention and split by PPI dose (low or high).

The analysis of the primary objective involves knowledge of the treatment and then knowledge of the factors used in the minimisation which will be available for everyone from the randomisation.

AspECT

A phase III randomised study of Aspirin and Esomeprazole chemoprevention in Barrett's metaplasia

Funded by CR-UK, MRC, UHL and NCI

ISRCTN No.85156844

Secondary endpoints –adenocarcinoma, high grade dysplasia, death
As described for primary but for each event separately.

Secondary endpoints – clinical and molecular risk factors

Available for a varying number of patients

Secondary endpoint - cost effectiveness

This endpoint is not being analysed by CSM

Secondary endpoints - changes in molecular markers and genomics

This endpoint is not being analysed by CSM

Secondary endpoints – quality of life

It was not possible to collect this data across time so this analysis cannot be done

Secondary endpoints – biological risk factors for cardiac disease and aspirin resistance

Cardiac events fulfilling a seriousness criterion will be noted as SAE and this will be used as indicative of cardiac disease. Biological risk factors of hypercholesterol, family history, patient's history, hypertension, diabetes and smoking will be tabled to show availability of this data.

Secondary endpoints – gender effect

Gender data should be available on all from randomisation

Sensitivity analysis – presence of helicobacter will be defined as helicobacter seropositivity at any point in the trial.

Pathology – local pathology results will be used

7. Patient Groups for Analysis

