Appendix 2: Variables to be used in analysis (Not exhaustive)

To check rand

VARIABLE	FORM
Length of Barrett's at rand or diagnosis	Randomisation or IR patient history
Age at rand	Randomisation
IM	

To describe sample

VARIABLE	FORM
Alcohol consumption	PR Patient history
Smoking history	PR Patient history
Cardiac history	IR Patient history
Duration of Barrett's pre randomisation	IR Patient history
Length of Barrett's at rand or diagnosis	Randomisation or IR patient history
Age at rand	Randomisation

Primary aim

VARIABLE	FORM
Length of Barrett's at rand or diagnosis	Randomisation or IR patient history
Age at rand	Randomisation
Rand date	Randomisation
Last follow-up date	Follow-up form
Date of death	
Cause of death	
Date high grade dysplasia	Endoscopy form or follow-up form
Date adenocarcinoma	Endoscopy form or follow-up form

Secondary aims

VARIABLE	FORM
Cardiac history	IR Patient history
Stage of cancer	Endoscopy report

Document History

Document history AspECT statistical analysis plan		
Ver	Date	Comments
0.1	16 th March 2006	First draft by [name]
0.2	21 st April 2006	Draft for review by [name]
0.3	12 th July 2006	Draft for review by rest of MSG support and [name]
0.4	18 th August 2006	Updated to Jan 2006 version of the protocol Added Info from 20 th July meeting with [name] Added comments/clarifications from 25 th July meeting with MSG support Passed to [name] and [name] to review and sign.
0.5	29 th Sept 2006	Passed to DSMC Added DMC comments Females randomised separately 100 Previous aspirin users to be entered
0.51	15 th August 2007	Added gender to the tables in section 6.2 Previous aspirin use deleted from tables in 6.2 since not collected since June 2007 on shortened forms Analysis of effect of high PPI by each event separately Analysis of effect of aspirin use by each event separately Randomisation to PPI arms only Clarification that Barretts length is at rand if available, otherwise it is at diagnosis Addition to appendix 2 – specifying data needed
0.52	20 th Nov 2007	Changed event list to clarify what cause-specific death means.
0.53	Jan 2008	Added version 9 important changes to randomisation
0.6	30thJan2008	Updated to version 9 of the protocol To be submitted to DSMC April 2008 Logo added on front page
0.7	May 2008	Name of file changed to CSM policy of statistical analysis plan

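### The secondary high grade dysplasia (HGD) outcome counts follow-up without endoscopy as HGD-free time: the HGD rate is understated, and the arm comparison is biased if endoscopy withdrawal differs by arm

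*SAP*

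**What the plan says.** SAP 2.7 defines the secondary HGD outcome as "Time from randomisation date to conversion from Barrett's metaplasia to high grade dysplasia (event) or time to last follow-up (no event"), and also ends time without an event when something such as death rules HGD out. The primary composite uses the same end date: "For patients who do not have one of these events of interest, the time from randomisation to date of last follow-up is calculated". SAP 6.5 repeats this. Appendix 2 lists "Last follow-up date" against the Follow-up form alone, and gives "Endoscopy form or follow-up form" as the source of the HGD date.

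Follow-up and endoscopy can separate. Protocol 6.2 provides for the patient who stops endoscopy: "If a patient absolutely cannot tolerate endoscopy every 2 years, or is removed by clinical decision from routine endoscopic screening". That patient may stay on trial medication and in trial follow-up, is still seen by the local investigator every two years, and is notified to the Trial Office. Protocol 5.1 adds: "The Patients may be followed up by telephone or in person at year 1, 3, 5, 7 and 9".

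SAP 6.6 says that "the endpoint of high grade dysplasia will be under represented due to those lost to follow-up". SAP 6.3 counts as defaulters only patients who attend no more trial visits. None of the sensitivity analyses in SAP 8.6 uses endoscopy dates, and no table of endoscopies by arm is planned. SAP 9 analyses HGD with an accelerated failure time model and with a competing-risks version of the Cox model.

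**The concern.** A Follow-up form shows that a patient is alive and in contact. It does not show that the oesophagus has been biopsied. A patient last endoscoped at year 4 who returns forms to year 8 adds eight years to the HGD denominator, but only four were covered by the examination that detects HGD.

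Two things follow. The HGD rate and cumulative incidence are too low in both arms. And if one arm stops endoscopy more often, that arm shows less HGD for reasons unrelated to treatment. Treatment is open (SAP 2.6.2), a clinical decision can end endoscopy, and endoscopies prompted by symptoms can yield events (SAP 2.2), so a difference could arise. HGD is a named secondary endpoint for both comparisons, and it is the one component of the composite that registry flagging does not supply. The caveat in SAP 6.6 covers patients lost to follow-up, not patients still followed without endoscopy.

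**Working it through.** The plan gives no figure for this bias. Its design figure (196 events, SAP 2.5.3) reproduces by Freedman's formula, 7.849 × (2.5/0.5)² = 196.2, but plays no part in what follows.

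**Inputs.** Death 1.16% per year (SAP 2.5.3). Endoscopy at years 2, 4, 6 and 8 (Protocol 5.1). Assumed, because the documents give no figure: HGD onset 0.5% per year; a share *w* who withdraw from endoscopy at a time uniform over years 2 to 6; forms to year 8; perfect detection at endoscopy; no detection after withdrawal. Protocol 13.2 offers only a planning statement that over 90% cope with repeated endoscopy.

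**By hand.** Of those who withdraw, half have their last endoscopy at year 2 and half at year 4, so on average 3 of 8 years are covered and 5/8 are not. Ignoring deaths, the understatement is about *w* × 5/8:
- *w* = 10%: 6.25%
- *w* = 20%: 12.5%
- *w* = 30%: 18.75%

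With no true effect, the rate ratio between arms is about (1 − 0.625*w*₁)/(1 − 0.625*w*₂):
- 10% v 5%: 0.9375/0.96875 = 0.97
- 20% v 10%: 0.875/0.9375 = 0.93
- 30% v 10%: 0.8125/0.9375 = 0.87
- equal stopping: 1.00

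**By simulation** (4 million patients per scenario, deaths included; rates per 100 patient-years; composite = HGD plus death):

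| Stop endoscopy | HGD, SAP rule | Relative to none stopping | HGD, censored at last endoscopy | Composite, SAP rule |
|---|---|---|---|---|
| 0% | 0.493 | 1.00 | 0.499 | 1.654 |
| 10% | 0.463 | 0.94 | 0.497 | 1.624 |
| 20% | 0.431 | 0.87 | 0.497 | 1.591 |
| 30% | 0.401 | 0.81 | 0.501 | 1.561 |

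HGD ratios: 0.431/0.463 = 0.93 and 0.401/0.463 = 0.87. Composite ratios: 1.591/1.624 = 0.98 and 1.561/1.624 = 0.96. For 10% v 5%, taking the 5% rates midway between the first two rows, HGD is 0.463/0.478 = 0.97 and the composite is 1.624/1.639 = 0.99. If adenocarcinoma at 0.85% per year (SAP 2.5.3) is added to death, giving 2.01%, the 30% v 10% composite ratio is (0.401 + 2.01)/(0.463 + 2.01) = 0.97.

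**Other assumptions.** With the last endoscopy equally likely at year 0, 2, 4 or 6, and HGD at 0.3, 0.6 or 1.0 per 100 patient-years, the understatement is again about 6%, 13% and 19%. If half of later HGD is still found, the ratios shrink to 0.97 (20% v 10%) and 0.94 (30% v 10%). Censoring at last endoscopy gives 1.00 throughout.

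**Form of the composite sensitivity analysis.** At 30% v 10% with no true effect:
- SAP rule: 0.96
- event-free patients censored at withdrawal, later deaths still counted: 1.07
- event-free patients censored at last endoscopy plus 27 months, later deaths still counted: 1.03
- time and events of all patients stopped at withdrawal: 0.99

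The second and third remove survivors' time but keep the deaths, which reverses the bias. The last leaves only the uncovered gap between last endoscopy and withdrawal.

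**The case against.** The strongest reply is that the HGD objective is comparative. Understatement shared equally by both arms leaves the ratio at 1.00, and nothing in the documents shows or predicts different endoscopy attendance by arm. That stands. A reader might infer that the arm with fewer endoscopies will look protected; the documents support only the conditional statement.

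The 20% and 30% scenarios also lie beyond the planning figure in Protocol 13.2, and Protocol 6.2 describes withdrawal from endoscopy narrowly. At 10% v 5% the effect is small.

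A reader might infer that nothing is known once endoscopy stops. That goes too far. An HGD date can come from a follow-up form, disease status and notes are checked yearly, the investigator still sees the patient, endoscopies for symptoms count, and SAP 5 checks any ablation, resection or oesophagectomy without a logged progression. The figures with no later detection are therefore upper bounds.

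A reader might also take the protocol's sentence on missed follow-up and endoscopy, "This will not affect the primary outcome as all-cause mortality and conversion to BA will be assessed by the Office of National Statistics", as a claim about HGD. It belongs to the original sample size statement, and its reason names only death and adenocarcinoma. The composite including HGD enters with the October 2008 statement, so the sentence needs no correction on this account.

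Appendix 2 says that it is not exhaustive, and the withdrawals reported under SAP 6.3 could include withdrawals from endoscopy. But the SAP does not say so, and a description of losses would not move the censoring date. The censoring rule itself is not answered.

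**Conclusion.** The point holds for the secondary HGD outcome. As written, the rule counts time without endoscopic surveillance as HGD-free, and no planned analysis or table corrects or reveals this. The HGD rate is at most about 6% to 19% too low if 10% to 30% of patients stop endoscopy. The between-arm ratio is distorted only under unequal stopping: about 0.97 to 0.87 across the scenarios examined, with the composite at 0.99 to 0.96. The stopping shares, their timing and the HGD rate are assumptions; the proportional understatement hardly depends on the HGD rate. Confidence is high for the rule and for the direction of the absolute error. Bias between the arms is a possibility to be checked in the data, not a finding.

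**What to change.** 1. SAP 2.7: censor event-free patients for the secondary HGD outcome at their last endoscopy with histology, or use an interval-censored method.
2. SAP 9, competing-risks model for HGD: apply one surveillance cut-off to every patient, for example withdrawal from endoscopy, so that deaths and event-free time after it are both excluded.
3. Keep the primary composite as defined, with its deaths and cancers.
4. SAP 8.6: add one composite sensitivity analysis that stops follow-up at withdrawal from endoscopy for all patients, so that later deaths and cancers are not counted as events. State that it assumes stopping is unrelated to risk.
5. Report by arm the number withdrawn from endoscopy and the share of follow-up time covered by endoscopy.
6. SAP 6.6: extend the statement on HGD under-ascertainment to patients still followed without endoscopy.

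Endoscopy dates are on the trial forms, and endoscopy withdrawals are notified to the Trial Office, so no new data are needed. The cost is SAP wording, one table, the changed HGD censoring and one extra model run, with less HGD person-time and slightly wider HGD intervals. Censoring HGD at the last endoscopy also assumes that stopping is unrelated to HGD risk, and the SAP should say so.
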